## PROTOCOL AMENDMENT SUMMARY OF CHANGES

Below are the details of the changes to the observation plan.

### DOCUMENT HISTORY

Document	Country/Countries impacted by amendment	Date, version
Amended Observational Protocol V2.0	All countries	29-Oct-2021, Version 2.0
Observational Protocol V1.0	All countries	09-Jan-2020, Version 1.0

### AMENDED PROTOCOL V2.0 (29-Oct-2021)

This amended Observational Protocol (V2.0) is considered to be nonsubstantial based on the criteria set forth in Article 10(a) of Directive 2001/20/EC of the European Parliament and the Council of the European Union because it does not significantly impact the safety or physical/mental integrity of participants, nor the scientific value of the study.

### OVERALL RATIONALE FOR THE AMENDMENT

Protocol amendment summary of changes table

Section # and Name	Description of Change	Brief Rationale
Names & Addresses of Study Management	[REDACTED]	New address as of mid of December 2021
Names & Addresses of Study Management	Global statistician changed to the local statistician	Global Statistician no longer available
Names & Addresses of Country Teams representative	[REDACTED]: Change of clinic address	[REDACTED] been working at the Johannes Wesling Klinikum Minden since 01.04.21
Names & Addresses of Country Teams representative	Instead of [REDACTED] is Country Team Representative in Switzerland	New Country Team Representative in Switzerland
Names & Addresses of Scientific Director	[REDACTED]: Change of clinic address	[REDACTED] been working at the Johannes Wesling Klinikum Minden since 01.04.21
Names & Addresses of Sponsor	Sanofi-Aventis GmbH, Österreich: [name]	Clarification of the name of the sponsor and new address as of 01.12.2021
1 Synopsis Scientific Committee Chair Person	Instead of [REDACTED] is Scientific Committee Chair Person in Switzerland	New Scientific Committee Chair Person in Switzerland
1 Synopsis Study Design and Duration	"Sanofi-ICF" is used instead of "ICF"	Clarification that the Sanofi-ICF is only required for the prospective cohort

Section # and Name	Description of Change	Brief Rationale
1 Synopsis Study Population Inclusion criteria	Retrospective Cohort: no Sanofi-ICF is needed	Clarification that the Sanofi-ICF is not required for the retrospective cohort
1 Synopsis Study Population Inclusion criteria	Retrospective Cohort: including patients who are no longer alive	Clarification that it is planned to include patients in retrospective cohort who are no longer alive
1 Synopsis Main Data Collected retrospective cohort	Retrospective Cohort: no Sanofi-ICF is needed	Clarification that the Sanofi-ICF is not required for the retrospective cohort
1 Synopsis Main Data Collected retrospective cohort	Retrospective Cohort: including patients who are no longer alive	Clarification that it is planned to include patients in retrospective cohort who are no longer alive
1 Synopsis Estimated Duration of the Study	FPI changed to 01.03.21, LPI changed to 01.03.23, LPO changed to 01.03.26	Adjustment of data after delayed enrollment of the 1st patient in Germany
7.2 Study Duration and Dates	FPI (start of documentation) changed to 01.03.21, LPI changed to 01.03.23, LPO (end of documentation) changed to 01.03.26, Data base lock changed to 01.05.26, estimated clinical study report changed to 01.01.27	Adjustment of data after delayed enrollment of the 1st patient in Germany
8.2 Selection of patients – Inclusion criteria	Retrospective cohort: Change of > 18 years to ≥ 18 years and including patients who are no longer alive	Correction and Clarification
8.3 Selection of patients – Exclusion criteria	Retrospective cohort: advCSCC of unknown primary origin	Inserting a missing paragraph
8.3 Selection of patients - Premature withdrawal from the study	no Sanofi-ICF is needed	Clarification that the Sanofi-ICF is not required for the retrospective cohort
9 Case Report Form (CRF) Definitions for the CRF – Clinical Outcomes	TTNT: Change from "start of next medication" to "start of next systemic therapy"	Clarification
13 Management and reporting of adverse events/adverse reactions	"Alcedis" instead of "Aldedis"	Correction of a spelling mistake
13.3 AE of special interest (AESI)	"CRO" instead of "r"	Correction of a spelling mistake
14.3.1.1 primary variable	Change from "start of next medication" to "start of next systemic therapy"	Clarification
	All next systemic treatments excluding BSC will be evaluated	Insertion of the sentence for further explanation

## 1 SYNOPSIS

COMPOUND: Cemiplimab (SAR439684)	
STUDY No: OBS16381	
TITLE	Two cohort registry study for patients with advanced CSCC treated with Cemiplimab or other approaches
LOCATION	Approx. 60 sites in Germany, plus 5 sites in Switzerland and 5 sites in Austria
SCIENTIFIC COMMITTEE CHAIR PERSON	[REDACTED]
STUDY OBJECTIVE(S)	
The objectives of the study are
 
Prospective cohort:
 

• To identify TTNT

• To identify potential determinants of disease progression as final outcome, Quality of life (QoL), pain and other health related outcomes for CSCC patients undergoing treatment with Cemiplimab

• To collect long-term effectiveness and describe effects of treatment

• To collect safety data in a real world setting

 
Retrospective cohort:
 

• To examine real-world data of advanced CSCC (advCSCC) patients who were treated before approval of Cemiplimab (treatment approaches, safety, patient characteristics, long-term effects)

 
Primary objective prospective and retrospective cohort:
 
Primary objective for this non-interventional study (NIS) is time to next treatment (TTNT) excluding best supportive care (BSC).
 
Secondary objectives prospective cohort:
 
Patient demographics and baseline characteristics (TNM stage), Cemiplimab treatment regimen, duration of treatment (DOT), prior and post Cemiplimab treatments, response to Cemiplimab treatment (ORR, CR, PR, SD), duration of response (DOR), disease control rate (DCR = CR+PR+SD), time to treatment failure (TTFT), overall survival (OS), progression free survival (PFS), safety data, quality of Life (QoL) incl. pain.
 
Secondary objectives retrospective cohort:
 
Patient demographics and baseline characteristics (TNM stage), effectiveness (ORR, PFS, OS) and safety of different treatment options used routinely for advanced CSCC prior to Cemiplimab launch, patterns

	of treatment.
STUDY DESIGN & DURATION	
This is a non-interventional multicenter study in Germany, Austria and Switzerland. The study includes two cohorts of adult patients with advCSCC who receive either treatment with Cemiplimab (prospective cohort) or other therapeutic approaches (retrospective cohort).
 
Enrollment will take place at approx. 70 study sites. The selection of participating sites will attempt to capture a representative sample of advCSCC treating clinic and office based physicians to get data from a real world setting outside of clinical trials.
 
In each cohort 200 patients will be enrolled from Germany, Austria and Switzerland. The duration of follow up will be up to 36 months for each patient in the prospective cohort.
 
Patients who meet the inclusion criteria and have signed the informed consent form (Sanofi-ICF) (only in the prospective cohort) will be included in the study.

STUDY POPULATION	
Inclusion Criteria
 
For the prospective cohort:
 
 
a. Planned treatment with Cemiplimab for advCSCC according to SmPC
 
b. Able to understand and complete study-related questionnaires
 
c. Signed ICF
 
 
For the retrospective cohort:
 
 
d. Patients <math>\geq</math> 18 years with first diagnosed advCSCC (locally advanced or metastatic CSCC) between Jan/2012 and Aug/2019
 
e. From these patients only anonymous data will be collected. Thus no Sanofi-ICF is needed This procedure allows including data from patients who are no longer alive (planned).
 
 
Exclusion Criteria
 
For the prospective cohort:
 
 
a. Missing ICF
 
b. advCSCC of unknown primary origin
 
c. Any condition that, in the opinion of the study physician, may interfere with patient's ability to participate in the study, such as severe cognitive impairment or other comorbidities that would, in the opinion of the study physician, predictably prevent the patient from adequately completing QoL assessments.
 

	
For the retrospective cohort:
 
 
d. Patients enrolled in clinical trials with Cemiplimab for advCSCC treatment
 
e. advCSCC of unknown primary origin
 
 
Sample Size: 400 patients (200 patients in each cohort)


RECRUITMENT MODALITIES
	
Selection of Physicians/sites
 
Study site selection will be performed independently in Germany, Austria and Switzerland.
 
This study will be conducted among sample representatives who are advCSCC-treating physicians (e.g., Dermatology- Oncologists, Oncologists, Surgeons). Physicians will be recruited from country-specific physician databases and ADOReg (ADO, Arbeitsgemeinschaft Dermatologische Onkologie; Reg, Registry).
 
Selection of patients
 
These physicians or their assigned staff will be responsible for patient chart identification, qualification and selection, data abstraction, completion of the patient eCRF, resolution of data queries and data validations.

STUDY TREATMENT
	
No investigational agents due to the non-interventional character of the study.
 
Patients may receive any therapies as deemed necessary by their treating physicians for the treatment of advCSCC or other comorbid conditions.

ENDPOINTS / OUTCOMES
	
Data will be summarized descriptively with consideration for the following outcomes of interest:
 
Primary Endpoint: Effectiveness
 
 
○ The primary endpoint is TTNT excluding best supportive care (BSC)
 
 
Secondary Endpoints: Health related outcomes and safety
 
 
○ Secondary endpoints include health related outcomes such as ORR, DOR, DCR, QoL, OS, PFS, pain and safety data.
 

MAIN DATA COLLECTED
	
Prospective cohort:
 
Each patient will be initially treated with Cemiplimab and documented during a follow up time of 36 months according to the usual follow-up in the routine practice.
 
Documentation will be performed up to 8 times:
 
 
• D1: Baseline
 
• D2: after approx. 3 months
 
• D3: after approx. 6 months
 
• D4: after approx. 9 months
 

- D5: after approx. 12 months
- D6: after approx. 18 months
- D7: after approx. 24 months
- D8: after approx. 36 months / end of the Study

In case of Cemiplimab treatment discontinuation in the eCRF at any time, the documentation will continue until D8 or patient's death to assess outcome and further therapeutic modalities, unless the patient withdraws the consent.

The collected data will include:

- Patient and Tumor Characteristics:
  - Demographics (Gender, age ect.)
  - Past medical history, regarding anti-tumor treatment prior to Cemiplimab,
  - Disease staging
  - Risk factors related to advCSCC progression and survival
- Survival:
  - advCSCC specific and overall mortality
- Treatment Patterns:
  - Interventions for advCSCC treatment (e.g., surgery, radiation, drug therapy, etc.) before initiation of Cemiplimab, if applicable
  - Patterns of recurrence
  - Determinants for disease sequela (recurrence, metastasis)
  -
- Patient Reported Outcomes:
  - Baseline QoL
  - Baseline health status
  - Impact of Cemiplimab on QoL based on EORTC QLQ-C30 questionnaire
- Response:
  - Time to next treatment (TTNT) or death
  - Objective response rate (ORR)
  - Progression free survival (PFS)
  - Disease Control Rate (DCR)
  - Duration of Response (DOR)
  - Duration of Treatment
  - Overall Survival (OS)
  - Immune-related adverse events (irAEs)
  - Serious adverse events (SAEs)
  - Disease Specific Death Rate (DSD)

**Retrospective Cohort:**

In the retrospective cohort this study will document (1 documentation time point) patients not intended for Cemiplimab therapy and first diagnosed with advCSCC between Jan/2012 and Aug/2019. It will obtain data of anti tumor therapies (prior to Cemiplimab approval) and

[figure not shown]
	
their outcome. We plan to document the disease history including prior surgery, radiotherapy, systemic therapies and the related safety data as well as effectiveness. The largest study with advCSCC was recently published (Hillen et al. 2018), which examined retrospectively 190 patients from Germany and Austria first diagnosed between Jan/2010 and Dec/2011 with a first-time follow-up on May/2014.
 
Within this retrospective cohort, we will collect only anonymous data from patients without Sanofi-ICF. This procedure allows including data from patients who are no longer alive (planned)
 
Patient characteristics (age, sex, diseases, immunosuppression, comorbidities, localization, etc.) and therapeutic modalities will be evaluated (as in the prospective cohort if applicable).
																				

STATISTICAL METHODOLOGY
	
Sample size justification
 
The primary objective of the study is to describe TTNT or death in 200 patients with advCSCC initially treated with Cemiplimab (prospective cohort) or 200 patients with other therapeutic approaches (retrospective cohort).
 
  
 Sample size	Number of event	Width of 95%CI	Median TTNT (months)	Lower limit 95% CI	Upper limit 95% CI	
   
 200	180	8.9	30.0	26.1	34.9	
 
 11.8	40.0	34.7	46.6	
 
 14.8	50.0	43.4	58.2	
  
 
References Mathews, Paul. 2010. Sample Size Calculations: Practical Methods for Engineers and Scientists. Mathews Malnar and Bailey, Inc.
 
Including 200 patients in each cohort produces a two-sided 95% confidence interval with a width equal from 8.9 to 14.8 when the expected median TTNT is respectively from 30 to 50 monts. The percent censoring is anticipated to be 10%.
 
Primary analysis
 
The primary analysis is descriptive. TTNT will be estimated and visualized for each cohort separately by Kaplan-Meier estimators. Median TTNT will be presented with 95%-confidence intervals. Potential predictors of TTNT will be analyzed using Cox proportional hazards regression.
 
Secondary analysis
 
All secondary outcomes will be analyzed descriptively.
 
The rate of ORR and 95%-CI will be given for each cohort. In addition
	Sample size	Number of event	Width of 95%CI	Median TTNT (months)	Lower limit 95% CI	Upper limit 95% CI	200	180	8.9	30.0	26.1	34.9	11.8	40.0	34.7	46.6	14.8	50.0	43.4	58.2
Sample size	Number of event	Width of 95%CI	Median TTNT (months)	Lower limit 95% CI	Upper limit 95% CI																
200	180	8.9	30.0	26.1	34.9																
		11.8	40.0	34.7	46.6																
		14.8	50.0	43.4	58.2																

	
and in an exploratory way, the pooled rate and its 95%-confidence interval will also be given. Potential predictors of response will be analyzed using logistic regression and/or Factorial Multiple Correspondences Analyses.
 
For time to event endpoints, Kaplan-Meier curves will be presented and median time to event will be estimated with corresponding 95%-confidence intervals.

ESTIMATED DURATION OF THE STUDY	
Prospective cohort: Estimated enrollment duration 24 months
 
Estimated dates:
 

○ First Patient In: 01.03.2021

○ Last Patient In: 01.03.2023

○ Last Patient Out: 01.03.2026

 
Retrospective cohort: Patients first diagnosed with advCSCC between Jan/2012 and Aug/2019 and not intended to receive Cemiplimab will be documented in the retrospective cohort once.

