#### **14.3.2 Statistical analyses**

##### **14.3.2.1 Primary analysis**

The primary analysis is descriptive. TTNT will be estimated and visualized for each cohort separately by Kaplan-Meier estimators. Median TTNT will be presented with 95%-confidence intervals. Potential predictors of TTNT will be analyzed using Cox proportional hazards regression.

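### The synopsis states 95% CI widths for median TTNT that match an exponential-model interval, not the planned Kaplan-Meier interval, which under that same model is roughly 35-40% wider

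*Protocol*

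**What the plan says.** The Protocol synopsis (section 1, Statistical methodology, sample size justification) tabulates precision for 200 patients and 180 events. The rows give width, median, lower limit and upper limit, in months: "8.9 30.0 26.1 34.9", "11.8 40.0 34.7 46.6" and "14.8 50.0 43.4 58.2". The text below the table reads "Including 200 patients in each cohort produces a two-sided 95% confidence interval with a width equal from 8.9 to 14.8". It ties the two ends of this range to assumed medians of 30 and 50 months, and adds "The percent censoring is anticipated to be 10" per cent. A general sample-size textbook is cited. Neither a survival distribution nor a formula is named.

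The cohort size is fixed in the same synopsis: "In each cohort 200 patients will be enrolled from Germany, Austria and Switzerland".

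The primary analysis is set in the synopsis and again in section 14.3.2.1: "TTNT will be estimated and visualized for each cohort separately by Kaplan-Meier estimators. Median TTNT will be presented with 95%-confidence intervals". No exponential or other parametric estimate of the median appears in the protocol. Section 8.1 says that no hypothesis is tested and refers back to the synopsis for the sample size justification.

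**The concern.** A confidence interval for a median can be obtained in two quite different ways. If event times are taken to be exponential, the median is a multiple of one rate parameter, and every observed event time helps to estimate it. A Kaplan-Meier median uses the height of the survival curve near 50% and its local slope, so later events add almost nothing. The first interval is narrower when the model is right, but it is the interval of a different estimator.

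If the table was built with the first method and the trial reports the second, the quoted precision is not a property of the planned analysis. The study tests no hypothesis, so precision of the median is what justifies 200 patients per cohort. Nothing about power or type I error is at stake.

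**Working it through.** **Inputs.** n = 200 per cohort; d = 180 events (10% censoring); medians m = 30, 40, 50 months; two-sided 95%. All are from the synopsis. The exponential distribution is an inference, tested in step 1.

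**Step 1: reproduce the table.** Exact interval for an exponential median: lower = 2dm / χ²(0.975; 2d), upper = 2dm / χ²(0.025; 2d). With 2d = 360 the quantiles are 414.46 and 309.33. For m = 30: 10800/414.46 = 26.06 and 10800/309.33 = 34.91.

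| Median | Computed limits | Computed width | Stated limits | Stated width |
|---|---|---|---|---|
| 30 | 26.06 to 34.91 | 8.86 | 26.1 to 34.9 | 8.9 |
| 40 | 34.74 to 46.55 | 11.81 | 34.7 to 46.6 | 11.8 |
| 50 | 43.43 to 58.19 | 14.76 | 43.4 to 58.2 | 14.8 |

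All nine figures match to rounding. Using 200 events, 2d+2 degrees of freedom for the lower limit, a Wald interval or a log-Wald interval does not match them all. The half-width is 14.8% of the median in every row.

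**Step 2: Kaplan-Meier interval, same assumptions, large-sample formula.** SE(median) = SE of S(m) / f(m), where f(m) = 0.5 × ln 2 / m.

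- *Random exponential censoring of 10%.* The censoring hazard is one ninth of the event hazard. Greenwood variance of S(m) = (0.25/200) × 0.9 × (exp(ln 2 × 10/9) − 1) = 0.00125 × 0.9 × 1.160 = 0.001305, so SE = 0.0361. Then SE(median) = 0.0361m / 0.3466 = 0.104m, and the width is 3.92 × 0.104m = 0.409m.
- *All censoring after the median.* SE of S(m) = 0.5/√200 = 0.0354, and the width is 0.400m.

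| Median | Stated | KM, random censoring | Ratio | KM, late censoring | Ratio |
|---|---|---|---|---|---|
| 30 | 8.9 | 12.3 | 1.38 | 12.0 | 1.35 |
| 40 | 11.8 | 16.3 | 1.38 | 16.0 | 1.36 |
| 50 | 14.8 | 20.4 | 1.38 | 20.0 | 1.35 |

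The half-width is 20.0-20.4% of the median.

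**Step 3: simulation** (2000 cohorts per setting; plain, log and log-log Greenwood intervals inverted at 50%). Mean widths at medians 30 / 40 / 50:

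- random censoring: 12.3-12.5 / 16.3-16.9 / 20.5-20.9 months (ratios 1.38-1.43);
- a common late cut-off leaving 10% censored: 11.8-12.2 / 15.6-16.2 / 19.5-20.2 months (ratios 1.32-1.37).

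The choice of transformation does not close the gap.

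**Step 4: dependence on the hazard shape.** With median 30, 10% random censoring and log-log intervals, Weibull shapes 0.8 / 1.0 / 1.2 / 1.4 / 1.5 give mean Kaplan-Meier widths of about 15.3 / 12.3 / 10.3 / 8.8 / 8.4 months. These shapes are assumptions; the protocol gives none.

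**Step 5: prospective cohort, follow-up capped at 36 months.** Expected events with exponential times are 200 × (1 − 2^(−36/m)) = 113, 93 and 79 for m = 30, 40 and 50, not 180. In simulation the upper Kaplan-Meier limit was not reached in about 53-59% of cohorts at median 30, and in nearly all or all at 40 and 50.

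**The case against.** The strongest defence has four parts.

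- *The table's arithmetic is right, and planning a nonparametric analysis with a simple parametric model is common.* The first half is true: a reader might infer a calculation error, and there is none. The second half does not rescue the statement. The synopsis presents the widths as what 200 patients produce, and under the table's own model the approximation errs towards optimism by about a third or more.
- *The excess holds only for a constant hazard.* This stands. At a Weibull shape of about 1.4 the Kaplan-Meier width at median 30 is close to the stated 8.9 months. That agreement would be a coincidence, since the exponential model behind the table would then be wrong; at shape 0.8 the gap is larger instead.
- *The reported interval need not be wider than stated.* This also stands. A reader might infer that the final interval is bound to be some 40% wider. The documents do not support that. The true median may lie outside 30-50 months. The introduction's only comparable figure is a PFS of 18.4 months in metastatic disease, a different endpoint; a median of that size would give 0.409 × 18.4 = 7.5 months under the same assumptions. In the prospective cohort the likelier outcome at the tabulated medians is no upper limit at all.
- *The study is descriptive and sets no maximum acceptable width.* True, so a reader would be wrong to infer that 200 patients per cohort are too few or that more are needed.

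Leaving the details to a statistical analysis plan does not settle it, because the protocol itself states both the widths and the estimator.

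**Conclusion.** The point holds as a mismatch between planning model and planned estimator. The stated widths of 8.9, 11.8 and 14.8 months are those of an exponential-model median with 180 events. For the planned Kaplan-Meier median under the same model, the widths average about 12, 16 and 20-21 months. The excess is roughly 35-40%, and 32-43% across all the censoring patterns and interval types tried.

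The conclusion rests on exponential times, which are inferred from the match of all nine figures rather than stated, and on 200 patients with about 180 events. It says nothing about whether those events can be reached. That is a separate matter, but it limits where corrected figures may be used: under the 36-month cap they cannot stand for the prospective cohort. The consequence is an overstated precision for the primary endpoint, worth correcting, and no threat to the validity of the analysis.

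**What to change.** In the synopsis, replace the widths and limits with those of the planned Kaplan-Meier interval (widths of about 12, 16 and 20-21 months), and state that they assume exponential times and 180 events.

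For the prospective cohort, do not carry over the 180-event widths. Compute the expected precision under the 36-month follow-up limit, or state that the upper confidence limit may not be reached.

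Section 14.1 separately claims a precision of 10%, defined as the half-length of the interval. Neither the exponential table (about 15%) nor the Kaplan-Meier interval (about 20%) meets it, so that sentence should be aligned in the same edit.

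The cost is one table and a few sentences. No patients or visits are added and the analysis does not change; the stated precision becomes less favourable.

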## Evidence for Cemiplimab in advCSCC

Substantial progress has recently been made in the development of immunotherapy for the treatment of cancer and specifically advCSCC. Checkpoint-blockade uses antibodies that impede immune inhibitory pathways such as programmed cell death 1 (PD-1) or PD-1 ligand 1 (PD-L1) interaction (Chang ALS, 2016). Efforts to characterize the genetic landscape of CSCC have been hampered by very high background mutation rates associated with UV damage which can be 5 to 15 times higher than what is found for non-cutaneous tumors. And with understanding the genomic signatures of aggressive CSCC it provides an opportunity to intensify upfront therapies in order to prevent the morbid consequences of treating advanced disease (Pickering 2014).

Cemiplimab is a high affinity, fully humanized, hinge stabilized IgG4P antibody against the PD-1 receptor that blocks the interaction of PD-1 with its ligands, PD-L1 and PD-L2 (Migden MR, 2018). Cemiplimab was approved by the FDA (Sep/2018) and by the EMA (June 28th 2019) for the treatment of adult patients with advCSCC who are no candidates for curative surgery or curative radiation [SmPC, Fachinformation LIBTAYO (Cemiplimab), September 2019], and is being studied in several other indications.

The efficacy of Cemiplimab in patients with mCSCC (nodal or distant) or ladvCSCC who were not candidates for curative surgery or curative radiation was evaluated in two open label, multicenter, non-randomized, multicohort studies: Study 1423 (NCT012383212) and 1540 (NCT01760498) (Kaplun H 2018, Papadopoulos KP 2016). Patients received Cemiplimab 3 mg/kg intravenously every 2 weeks for up to 48 weeks in study 1423 and up to 96 weeks in study 1540. In study 1540 one group with mCSCC patients were treated with a fix dose of 350mg every 3 weeks. The major efficacy outcome measure was confirmed by ORR. The efficacy analysis was conducted when all patients had the opportunity for at least 6 months of follow up. At the time of data cut-off (October 27th 2017) 47% of patients with mCSCC showed an objective response to Cemiplimab in study 1540, with a mean observed time to response of 1.9 months. The ORR in 76 locally advCSCC was 43.6% (data cut-off October 10th 2018) (Migden et al., ASCO 2019). At the time of data cut-off (September 20th 2018) PFS was 18.4 months in 59 mCSCC treated with cemiplimab (Guminski et al., ASCO 2019).

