## **7.2 DURATION OF STUDY PARTICIPATION FOR EACH PATIENT**

In the prospective cohort the data will be recorded during a follow-up of 36 months, beginning after study inclusion.

In the retrospective cohort we will document at one time point patients not intended for Cemiplimab therapy, who were first diagnosed advCSCC between Jan/2012 and Aug/2019. QoL data will be collected from patients within the prospective cohort. It is planned to perform yearly interim analyses and a final report at the end of the study.

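### For the prospective cohort, the synopsis precision table assumes 180 of 200 events at median TTNT of 30 to 50 months, which 36 months of follow-up per patient cannot yield

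*Protocol*

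**What the plan says.** The sample size justification is in the protocol synopsis, under Statistical Methodology; section 8.1 refers the reader there for the detail. It states: "Including 200 patients in each cohort produces a two-sided 95% confidence interval with a width equal from 8.9 to 14.8" months, where the "expected median TTNT is respectively from 30 to 50 monts". The first table row reads "200 180 8.9 30.0 26.1 34.9": sample size, events, interval width, median, lower and upper limit. The same 200 patients and 180 events serve the rows for medians of 40 and 50 months. The text adds: "The percent censoring is anticipated to be 10" per cent, which is the 20 of 200 patients without an event.

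On follow-up, the synopsis (Study Design & Duration) says: "The duration of follow up will be up to 36 months for each patient in the prospective cohort". Section 7.2 says: "In the prospective cohort the data will be recorded during a follow-up of 36 months, beginning after study inclusion". Section 8.3 (Study completion) ends participation at three years, at withdrawal of consent or at death. The dates in section 7.2 agree: last patient in on 01.03.2023 and last patient out on 01.03.2026.

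Section 14.3.2.1 plans a Kaplan-Meier estimate of TTNT for each cohort separately, and the median with its 95% confidence interval.

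**The concern.** A prospective patient who has neither started another systemic therapy nor died by month 36 is censored. With a median of 40 or 50 months that is more than half the cohort, and with a median of 30 months it is not far below half. A 10% censoring share cannot hold together with those medians and that follow-up, and the protocol nowhere reconciles them.

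The study tests no hypothesis, so the precision of the median is the whole rationale for 200 patients per cohort. If the planning medians are right, readers are promised an interval for the cemiplimab cohort that the design cannot deliver, and the median or its upper limit may not be estimable when the study reports.

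**Working it through.** **Inputs.** From the synopsis: n = 200 per cohort, r = 180 events, medians M = 30, 40, 50 months, two-sided 95% interval. From the synopsis, section 7.2 and section 8.3: follow-up of 36 months. Assumptions: exponential TTNT, start of cemiplimab and study inclusion taken as the same date, and no loss before month 36 unless stated.

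**Step 1: reproduce the table.** The exact exponential interval for a median is M × 2r / χ²(0.975; 2r) to M × 2r / χ²(0.025; 2r). With r = 180 the multipliers are 360/414.46 = 0.8686 and 360/309.33 = 1.1638.

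| M | Computed limits | Computed width | Stated |
|---|---|---|---|
| 30 | 26.06 to 34.91 | 8.86 | 26.1 to 34.9; 8.9 |
| 40 | 34.74 to 46.55 | 11.81 | 34.7 to 46.6; 11.8 |
| 50 | 43.43 to 58.19 | 14.76 | 43.4 to 58.2; 14.8 |

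Every cell agrees to rounding. The arithmetic is right; the input r = 180 is what needs checking.

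**Step 2: events within 36 months.** The event share is 1 − 2^(−36/M), and expected events are 200 times that. The last column puts these events into the Step 1 formula.

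| M | Event share | Events | Censored | Exponential interval (width) |
|---|---|---|---|---|
| 30 | 0.565 | 112.9 | 43.5% | 25.2 to 36.4 (11.2) |
| 40 | 0.464 | 92.8 | 53.6% | 33.0 to 49.6 (16.6) |
| 50 | 0.393 | 78.6 | 60.7% | 40.6 to 63.2 (22.6) |

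With an assumed extra 10% loss over 36 months, events fall to 108, 89 and 75.

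**Step 3: what 10% censoring would require.** Setting 2^(−36/M) = 0.10 gives M = 36 × ln 2 / ln 10 = 10.8 months. Holding M fixed instead, the follow-up needed is M × ln 10 / ln 2 = 100, 133 and 166 months per patient.

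**Step 4: the planned Kaplan-Meier analysis.** With no loss before month 36, the number of events by then is binomial (200, event share). The median is reached when at least 100 events have occurred. The upper 95% limit (log-log) is reached when at least 114 have occurred.

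| M | Median reached | Upper limit reached |
|---|---|---|
| 30 | 97% | 47% |
| 40 | 17% | 0.2% |
| 50 | 0.1% | 0% |

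A simulation of 4,000 studies agrees (98%, 18% and 0.2%; 48%, 0.3% and 0%).

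**Step 5: how far this depends on the model.** A true median of 40 or 50 months leaves more than half the patients event-free at month 36 whatever the distribution. With a true median of 30, 100 of 200 are event-free at month 30, so 180 events by month 36 would need 80 of those 100 to have an event within six months.

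**The case against.** Four points on the other side have weight.

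- **The consequence is conditional.** It follows only if true median TTNT is about 30 months or more. The protocol's introduction reports that "PFS was 18.4 months in 59 mCSCC treated with cemiplimab". PFS is not TTNT, so this is illustrative only. At a median of 18.4 months the same model gives about 148 events and a width of about 6.0 months. At 24 months it gives about 129 events and about 8.4 months, with the upper limit reached in about 99% of studies. A reader might infer that the primary estimate will fail. The documents do not support that; they show that the planning assumptions conflict with each other.
- **The median is not the only primary output.** Section 14.3.2.1 also plans the full Kaplan-Meier curve, which stays valid under heavy administrative censoring. Nor is a median above 36 months strictly out of reach in a given sample: with a true median of 40, the estimated median falls within 36 months in about 17% of studies.
- **The table also serves the retrospective cohort.** A reader might infer that it is equally wrong there. That does not follow, because no 36-month cap is stated for that cohort. Assuming uniform diagnosis dates, TTNT counted from diagnosis and no loss, documentation between March 2021 and March 2023 would give 145–169, 127–152 and 112–137 events; documentation in March 2026 would give 186, 174 and 162. The protocol does not fix enough to settle it.
- **The study is descriptive, and further summaries may be left to the SAP.** The absence of landmark estimates from the protocol is therefore not an error. The event count and censoring share are nevertheless printed in this document, and no SAP choice can reconcile them with the follow-up.

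Longer observation of early enrollees does not rescue the table. Section 8.3 sets completion at three years. Even if every patient were followed to 01.03.2026 (36 to 60 months, uniform entry assumed), expected events would be about 133, 112 and 97.

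**Conclusion.** The point holds for the prospective cohort, as a conflict between planning assumptions and not as an arithmetic error. At the stated medians, 36 months of follow-up gives about 113, 93 and 79 events where the table has 180, and 44%, 54% and 61% censoring where it has 10%. Even under the exponential model the intervals are 27%, 41% and 53% wider than stated (11.2/8.86, 16.6/11.81 and 22.6/14.76). Under the planned Kaplan-Meier analysis the interval often has no upper limit at a median of 30, and almost never has one at 40 or 50.

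The exact counts rest on exponential TTNT, which is the model that matches the protocol's own figures, and on no loss to follow-up, which favours the plan. That 180 events cannot be expected at medians of 40 and 50 needs no model. How often the median is reached depends on the planning medians being true.

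**What to change.** Split the synopsis justification by cohort.

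- **Prospective cohort.** Restate expected events and censoring for 36 months. Give an interval for the median only in the 30-month row (about 11.2 months wide under the exponential model), with a note that the Kaplan-Meier upper limit may not be reached. State that medians above 36 months are not estimable. Exponential widths for 40 and 50 months should not be printed, since the planned analysis would not deliver them.
- **Stated precision.** Base it on the Kaplan-Meier event-free probability at 12, 24 and 36 months, reported alongside the median. At a probability of 50% the half-width is 1.96 × √(0.25/200) = 6.9 percentage points; with 10–20% loss it is about 7.1 to 7.3.
- **Retrospective cohort.** Add a separate row based on that cohort's own follow-up, with the assumed start and end of observation stated.

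This needs no more patients, visits or follow-up. The cost is revised wording, a few extra table rows, and a stated precision less favourable than the present one.
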